10.11 Length of disease control

Measured from date of randomization to date of the first of the following events: progression such that the participant cannot receive protocol surgery, protocol surgery that does not render the participant disease-free, relapse after surgery that did render a participant disease-free, death due to any cause; participants last known to be alive without any of these events will be censored at the date of last contact.

10.12 Length of loco-regional control

Measured from date of randomization to date of the first of the following events: progression such that the participant cannot receive protocol surgery, protocol surgery that does not render the participant disease-free, relapse at the primary site and pre-randomization defined regional nodal basins after surgery that did render a participant disease-free; participants last known to be without any of these events will be censored at the date of death or date of recurrence outside of the primary site or pre-randomization defined nodal basin, whichever comes first.

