- d. **Progression:** One or more of the following must occur: 20% increase in the sum of appropriate diameters of target measurable lesions over smallest sum observed (over baseline if no decrease during therapy) using the same techniques as baseline, as well as an absolute increase of at least 0.5 cm. Unequivocal progression of non-measurable disease in the opinion of the treating physician (an explanation must be provided). Appearance of any new lesion/site. Death due to disease without prior documentation of progression and without symptomatic deterioration (see [Section 10.2e](#)).

Notes regarding new lesions: FDG-PET imaging can complement regular scans in identifying new lesions according to the following algorithm.

1. Negative FDG-PET at baseline, with a positive FDG-PET at follow-up is a sign of progression based on a new lesion.
 2. No FDG-PET at baseline and a positive FDG-PET at follow-up corresponding to a potential new site of disease must have a confirmation by anatomical assessment (e.g. CT, MRI, x-ray) as new site of disease to be considered progressive disease. In such a case, the date of progressive disease will be the date of the initial abnormal FDG-PET.
- e. **Symptomatic deterioration:** Global deterioration of health status requiring discontinuation of treatment without objective evidence of progression. Efforts should be made to obtain objective evidence of progression after discontinuation.

f. **Assessment inadequate, objective status unknown.** Progression or symptomatic deterioration has not been documented, and one or more target measurable lesions have not been assessed or inconsistent assessment methods were used.

g. **Objective status notes**

1. Non-measurable and non-target measurable disease do not affect Objective Status in determination of CR (must be absent--a participant who otherwise has a CR, but who has non-measurable or non-target measurable disease present or not assessed, will be classified as having a PR). However, non-measurable and non-target lesions are included in determination of progression (if new sites of disease develop or if unequivocal progression occurs in the opinion of the treating physician).
2. An objective status of PR or stable cannot follow one of CR. Stable can follow PR only in the rare case that tumor increases too little to qualify as progression, but enough that a previously documented 30% decrease no longer holds.

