11.5 Data and Safety Monitoring

A Data and Safety Monitoring Committee will oversee the conduct of the study. The Committee consists of four members from outside of the SWOG, 3 SWOG members, 3 non-voting representatives from the National Cancer Institute (NCI), and the Group Statistician (non-voting). The members of this Committee will receive confidential reports every 6 months from the SWOG Statistical Center and will meet at the Group's bi-annual meetings as necessary. The Committee will be responsible for decisions regarding possible termination and/or early reporting of the study.

In addition to the above DSMC review, toxicity and accrual monitoring are done routinely by the Study Chair, study Statistician, and the Disease Committee Chair. Endpoint monitoring is done by the study Statistician and Study Chair. Accrual reports are generated weekly, and formal toxicity reports are generated every 6 months. In addition, the Statistical Center, Adverse Event Coordinator at the Operations Office, SAE Physician Reviewer, and Study Chair monitor toxicities on an ongoing basis.

After 20, 40, and 60 eligible participants are randomized to the neoadjuvant arm, the following proportions will be tabulated and provided to the DSMC: 1) proportion of participants who develop a higher disease stage (i.e., are upstaged) between randomization and surgery, 2) proportion of participants who become unresectable prior to surgery, and 3) proportion of participants who become ineligible for surgery due to toxicity. At each analysis, we will evaluate whether any of the proportions crosses one of the following thresholds: 1) proportion of participants who develop a higher disease stage (i.e., are upstaged) between randomization and surgery is greater than 25%, 2) proportion of participants who become unresectable prior to surgery is greater than 16%, or 3) proportion of participants who become ineligible for surgery due to toxicity is greater than 5%. If any proportion crosses the corresponding threshold, accrual to the study will be suspended while the study team reviews and evaluates the data from the neoadjuvant arm. Accrual will only re-open after the DSMC reviews the study team evaluation and approves any protocol modifications if proposed.

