Radiology reports from all scans performed to assess disease (uploaded via the Source Documentation: Follow-Up Form in Rave®).

Off Treatment Notice documenting reasons for off treatment

If participant will not receive surgery on protocol, submit the Notice that Participant Will Not Receive Protocol Surgery

c. **STEP 3 REGISTRATION: PEMBROLIZUMAB (MK-3475)**

1. WITHIN 15 DAYS AFTER EACH CYCLE OF TREATMENT (1 CYCLE = 3 WEEKS):

Submit the following:

S1801 Treatment Form

S1801 Adverse Event Form

2. WITHIN 15 DAYS AFTER EACH DISEASE ASSESSMENT (SEE STUDY CALENDAR FOR SCHEDULE) UNTIL RECURRENCE (AS DEFINED IN SECTION 10.0) OR 5 YEARS AFTER RANDOMIZATION (WHICHEVER OCCURS FIRST):

Submit the following:

S1801 Post-Surgery Disease Assessment Form

Radiology reports from all scans performed to assess disease (uploaded via the Source Documentation: Follow-Up Form in Rave®).

3. WITHIN 15 DAYS OF DISCONTINUATION STEP 2 OF PROTOCOL TREATMENT:

Submit the following:

Off Treatment Notice documenting reasons for off treatment

S1801 Treatment Form

S1801 Adverse Event Form

d. **FOR ALL REGISTRATION STEPS:**

1. ONCE OFF ALL PROTOCOL TREATMENT, SUBMIT EVERY 6 MONTHS FOR 2 YEARS (SEE STUDY CALENDAR FOR SCHEDULE), THEN YEARLY THROUGH YEAR 10:

S1801 Follow-Up Form

S1801 Late Adverse Events Form

2. WITHIN 15 DAYS AFTER PROGRESSION OR RELAPSE:

Submit the following:

S1801 Follow-Up Form

Site(s) of progression/relapse Form

Radiology reports from all scans performed to assess disease (uploaded via the Source Documentation: Follow-Up Form in Rave®).

3. WITHIN 30 DAYS AFTER KNOWLEDGE OF DEATH:
Submit the Notice of Death, and all of the items listed in [Section 14.3d.1](#) (if the participant was still on protocol treatment) or the Follow-Up Form (if the participant was off protocol treatment) documenting death information.

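### The loco-regional control endpoint (10.12) counts distant-only spread that prevents surgery as a loco-regional failure but censors distant-only recurrence after surgery, which can bias the arm comparison against neoadjuvant

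*Combined protocol and SAP*

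**What the plan says.** Objective 1.2b compares loco-regional control in the surgical site(s) between arms. Section 11.4 does so with Kaplan-Meier estimates, log-rank tests and Cox models, and states no significance level for secondary endpoints.

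Section 10.12 has three failure components, and its list opens "progression such that the participant cannot receive protocol surgery, protocol surgery that does not render the participant disease-free, relapse at the primary site". The first two components name no site. The third does, and in full it is "relapse at the primary site and pre-randomization defined regional nodal basins after surgery that did render a participant disease-free". Anyone with no listed event "will be censored at the date of death or date of recurrence outside of the primary site or pre-randomization defined nodal basin, whichever comes first".

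Progression is not confined to known disease. Section 10.2(d) includes "Appearance of any new lesion/site", and Section 10.4 defines progression before surgery through RECIST 1.1 without reference to site.

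For comparison, Section 10.11 (disease control, an all-site endpoint) opens with essentially the same two components, and its censoring sentence reads "participants last known to be alive without any of these events will be censored at the date of last contact". Sections 10.10 (EFS) and 10.13 (OS) also censor at last contact. Section 10.12 does not mention it.

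**The concern.** Take two participants with the same disease course: regional nodes stable or shrinking, and new liver metastases at about Week 9.

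- On the neoadjuvant arm the metastases are found at the pre-surgery scan and surgery is cancelled. Section 10.12 records a loco-regional failure. The censoring clause does not help, because it covers only participants with no listed event.
- On the adjuvant arm the nodes have already been resected and the participant was rendered disease-free. The metastases are a recurrence outside the primary site and basins, so Section 10.12 censors.

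The same distant event is thus a failure or a censoring according to whether surgery came first, and the arms differ by design in when surgery comes. The planned test could show worse loco-regional control on the neoadjuvant arm when true loco-regional control is equal.

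A smaller gap is that a participant alive without any recurrence has no censoring date under the literal rule.

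**Working it through.** The documents state no rate, power or sample size for loco-regional control, so there is no figure of the plan's to reproduce.

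**1. Time at risk before surgery**
- Adjuvant arm (7.2c): 17 days to Step 2 plus 17 days to surgery = at most 34 days.
- Neoadjuvant arm (7.2d), taking dose 1 at randomization: dose 3 at 2 × 21 = day 42; surgery recommended within 21 days, so by about day 63; Week 12 is day 84. Section 7.4 requires a scan at Weeks 7 to 12.
- Ratio: 63/34 = 1.9 to 84/34 = 2.5.

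**2. Effect on the log-rank test (simulation, assumed rates)**

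Inputs from the plan: 336 eligible participants (11.3), so 168 per arm. My assumptions: equal true loco-regional failure of 15% at 2 years; other recurrence or death 20% at 2 years; follow-up uniform from 0.5 to 3.5 years; two-sided 5% test; distant-only spread at Weeks 7 to 12 equally common on both arms. On the neoadjuvant arm it prevents surgery and is recorded as failure. On the adjuvant arm it is censored.

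| Distant-only spread | Mean recorded failures, adjuvant / neoadjuvant | Rejection rate |
|---|---|---|
| 1% | about 22 / 24 | 5% |
| 2% | about 22 / 25 | 7% |
| 4% | about 21 / 28 | 15% |

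At 4%, nearly all rejections go against neoadjuvant.

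The result depends on how adjuvant-arm distant disease found at the Step 3 scan is classified. If half of it is recorded as surgery that did not render the participant disease-free, the rejection rates become about 5%, 5% and 8%. If all of it is, they stay at 4% to 6%.

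**3. A second set of assumptions**

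Follow-up uniform from 0.5 to 3 years, no other competing events, and 2-year loco-regional failure of 20% to 10% (ranges in that order):
- Surgery-preventing distant-only progression 2% neoadjuvant, 0% adjuvant: apparent hazard ratio 1.11 to 1.22, rejection 7% to 9%.
- 4% neoadjuvant, 1% adjuvant: hazard ratio 1.17 to 1.33, rejection 9% to 14%.
- Same scenarios with pre-surgery distant-only progression censored, as it is after surgery: hazard ratio about 1.0, rejection about 5%.

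**4. Where 1% sits against the plan's own model**

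Under 11.2 the neoadjuvant arm has 30% not long-term survivors, with median EFS 2.5 years. Events by day 84 (0.23 years): 0.30 × (1 − 2^(−0.23/2.5)) = 0.30 × 0.062 = 1.9%. If about half were distant-only, the rate would be near 1%. This is an orientation point, not an estimate.

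**5. Missing censoring date**

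At 104 EFS events (11.2) among 336 participants, 336 − 104 = 232 (69%) are EFS-event-free, so they have neither a death nor a recurrence to supply a date. Some EFS events are administrative (for example, not starting adjuvant therapy within 84 days), so the number without a date could be somewhat higher.

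**The case against.** **Unresected disease is not controlled disease.** The two participants above are not in the same loco-regional state, since one still has nodal tumour in place. Counting a participant who never reached surgery as lacking control at the surgical site is a defensible endpoint. But Section 10.12 does not follow that logic: surgery missed through toxicity or choice is not an event, only surgery missed through progression. Nor does the logic explain counting distant residual disease after the regional disease has been fully resected.

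**The adjuvant arm has its own route to failure.** Section 5.3 requires imaging within 42 days before Step 3, and Step 3 may be up to 84 days after surgery, so as late as day 34 + 84 = 118. Distant disease on that scan could be read as surgery that did not render the participant disease-free. This stands. It shrinks the bias, and could remove it if applied to every such case, but the text does not settle the classification.

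**Stronger readings that the documents do not support**
- A reader might take the 16% unresectability figure in Section 11.5 as a guide and infer a large distortion. It is a monitoring threshold that suspends accrual, not an expected rate. The distant share of relapses in the background section concerns Stage III relapse, not pre-surgical progression.
- A reader might infer that all distant spread before surgery counts. The first component applies only to progression that prevents protocol surgery. Distant disease that is also fully resected escapes both of the first two components.
- A reader might infer that most participants would drop out of the analysis for want of a censoring date. Last contact is the obvious default, it is used in the sibling endpoints, and any analyst would supply it.

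**Conclusion.** The inconsistency is in the text: distant-only disease is a loco-regional failure before surgery and a censoring after disease-free surgery, which fits poorly with an objective about control in the surgical sites. The direction of any bias is against neoadjuvant. That is an inference from the longer pre-surgery window and the required scan, since the documents give no rate by arm.

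The size is unknown. At assumed distant-only rates of 1% to 4%, false rejection runs from about 5% (no inflation) to about 15%, and is lower to the extent that adjuvant-arm distant disease at Step 3 is counted as failure. These figures rest on the assumed event rates, follow-up and 5% level.

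This is a secondary endpoint, and the primary EFS analysis is unaffected. The definition should be corrected because a planned between-arm comparison depends on it and the correction is cheap. The missing last-contact date is an editorial omission.

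**What to change.** In Section 10.12 and the derivation program:

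- **(a) One site set throughout.** Apply it to all three components and to the censoring clause: the primary site, the pre-randomization regional basins and, if the objective's reference to surgical sites is meant to include them, the other sites on the Planned Surgery Form. The last group matters because resectable Stage IV and satellite or in-transit disease are eligible. Progression that prevents surgery, and residual disease after surgery, would count only when at those sites.
- **(b) Same treatment before and after surgery.** Make distant-only progression a competing event in both periods and report cumulative incidence by arm. Do not simply censor participants whose nodal disease remains in place, because that censoring would be informative and would favour neoadjuvant. List participants left unresected separately by arm, and keep the current all-site definition as a sensitivity analysis.
- **(c) Last contact.** Add the date of last contact to the censoring clause, to match 10.10, 10.11 and 10.13.

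Cost: wording and programming. Section 14.3 already collects the "Site(s) of progression/relapse Form" after progression or relapse, so sites of progression need no new data. The downside is fewer recorded loco-regional events, and participants unresected because of distant spread would no longer count as loco-regional failures in the main analysis. The separate listing and the sensitivity analysis keep them visible.

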10.13 Overall Survival

Measured from date of randomization to date of death due to any cause. Participants known to be alive are censored at date of last contact.

10.14 Performance Status

Participants will be graded according to the Zubrod Performance Status Scale.

POINT	DESCRIPTION
0	Fully active, able to carry on all pre-disease performance without restriction.
1	Restricted in physically strenuous activity but ambulatory and able to carry out work of a light or sedentary nature, e.g., light housework, office work.
2	Ambulatory and capable of self-care but unable to carry out any work activities; up and about more than 50% of waking hours.
3	Capable of limited self-care, confined to bed or chair more than 50% of waking hours.
4	Completely disabled; cannot carry on any self-care; totally confined to bed or chair

11.0 STATISTICAL CONSIDERATIONS

11.1 Accrual goals

Based on **S1404** accrual, 43% of **S1404** participants would have been eligible for this neoadjuvant protocol. **S1404** has enrolled an average 80 participants/month. Not all sites participating in **S1404** will necessarily participate in this trial, so we anticipate that approximately 24 participants/month would enroll in this trial.

11.2 Analysis plan and sample size justification for primary objective

Based on EFS trends in this participant population, we will use exponential-mixture cure models to describe EFS patterns in the arms. Based on Weber 2017, we assume that on the adjuvant pembrolizumab (MK-3475) arm (null hypothesis) 60% participants will be long-term survivors (or cured or not observed to have an event during the finite follow-up of the trial) and that median EFS for participants who are not long-term survivors will be 2 years. We power this study to detect an alternative EFS in the neoadjuvant arm with 70% of participants being long-term survivors and median EFS among those who are not long-term survivors of 2.5 years. We note that these survival patterns do not follow a proportional hazards assumption and that average hazard ratios from Cox models are expected to become more null with additional follow-up.

We assume 1:1 randomization, accrual over 2 years, and up to 10 years of follow-up after randomization. Under these assumptions the average hazard ratio under the alternative is 0.64. Under the alternative, with a sample size of 500 eligible participants (250/arm), 100% of expected events is 104 events across both arms. At 50% of expected events (51 events, expected approximately when accrual completes), we will perform a futility test testing the alternative hazard ratio from a Cox regression model at the one-sided 2.5% level. No formal interim test of efficacy will be performed. Under the null hypothesis the probability of stopping early for futility is 45% and under the alternative is 2%. The final analysis will consist of a log-rank test of the null hypothesis at the two-sided 15% level (expected 1.5 years after accrual completes). The power of this design is 81%.

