The current standard of care has been set by the recently reported CheckMate-238 study, and the FDA has approved the use of nivolumab for completely resected node-positive or metastatic melanoma. (10) Nivolumab and pembrolizumab (MK-3475) have never been tested head-to-head but results from clinical trials in metastatic melanoma demonstrate equitable outcomes with these two agents. Ongoing adjuvant clinical trials in patients with melanoma include **S1404** (pembrolizumab (MK-3475) versus choice of standard of care), KEYNOTE-054 (pembrolizumab (MK-3475) versus placebo), and CheckMate-915, a randomized, Phase III, double-blind study of nivolumab versus the combination of nivolumab plus ipilimumab in patients with resected, Stage III melanoma). As of May 2018, KEYNOTE-054 data demonstrated that adjuvant pembrolizumab is associated with an improved 1-year and 18-month recurrence-free survival (RFS) compared to placebo. (11) The data have not yet matured to produce distant metastasis-free survival and overall survival results.

Biological rationale for the study population based on the anticipated mechanism of action of pembrolizumab (MK-3475):

Patients with bulky resectable melanoma have been treated using a neoadjuvant approach with chemotherapy, targeted therapy, and more recently, checkpoint blockade at multidisciplinary academic medical centers. Studying systemic treatment in this resectable population offers insight into biologic and pathologic response to treatment. It also provides an intact tumor-infiltrating lymphocyte population upon which checkpoint blockade often has its greatest effects in antigen presentation and generation of an anti-tumor immune response. While adequate and effective surgery is the goal of early treatment of primary melanoma, some cases with bulky nodal involvement are at high risk of local or distant recurrence despite upfront surgical resection. Neoadjuvant treatment further offers the benefit of an early on-treatment pathological sample that can be profiled for additional biomarkers and correlated with survival.

Inclusion of Women and Minorities

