10.10 Event-Free Survival

Measured from date of randomization to date of first: documentation of progression that renders participant unable to receive planned protocol surgery, off protocol therapy for any reason without subsequent protocol surgery (with one exception noted below), failure to begin adjuvant therapy within 84 days after surgery, relapse after surgery or death due to any cause. Participants last known to be alive and event-free are censored at date of last contact. On both arms, all participants who do not register for adjuvant therapy (for whatever reason) will be assigned the event time of 84 days.

Patients treated on the neo-adjuvant arm who achieve an unconfirmed PR or CR (per RECIST 1.1) at the first protocol disease assessment and choose not to undergo protocol surgery will not be counted as an event if the PR or CR is confirmed prior to starting any non-protocol therapy other than pembrolizumab. Such patients will not have an event when not receiving protocol surgery, and their EFS will be measured from the date of randomization to the first of relapse or death due to any causes with patients last known to be alive without relapse censored at the date of last contact. All other patients who do not receive protocol surgery will be assigned the EFS event time of 84 days.

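### The 81% power rests on EFS curves with no stated allowance for the day-84 events that Section 10.10 creates, and Section 11.3's event timing does not fit those curves

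*Combined protocol and SAP*

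**What the plan says.** Section 11.2 describes EFS by exponential-mixture cure models. On the adjuvant arm "60% participants will be long-term survivors (or cured or not observed to have an event during the finite follow-up of the trial"), and "median EFS for participants who are not long-term survivors will be 2 years". The neoadjuvant alternative is "70% of participants being long-term survivors and median EFS among those who are not long-term survivors of 2.5 years". "The final analysis will consist of a log-rank test of the null hypothesis at the two-sided 15% level", at 104 events in 500 participants with an average hazard ratio of 0.64. "The power of this design is 81" percent. Section 11.3 cuts the sample to 336, keeps the same EFS assumptions and alpha, claims the same power, and expects full events within six months of the end of accrual.

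The control curve is attributed to the cited adjuvant nivolumab trial. Section 2.0 says of the standard set by that trial that "the FDA has approved the use of nivolumab for completely resected node-positive or metastatic melanoma".

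Section 10.10 starts the EFS clock at randomization, which comes before surgery on both arms. It then says that "all participants who do not register for adjuvant therapy (for whatever reason) will be assigned the event time of 84 days", and gives the same time to participants without protocol surgery. There is one exception: neoadjuvant participants with a PR or CR at the first assessment who decline surgery, provided the response is later confirmed. Under Section 5.3, R2 resections cannot enter Step 3, so they fall under the day-84 rule too.

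**The concern.** The endpoint has a step at day 84; the planning curve has none. A curve based on completely resected patients starting adjuvant treatment would not contain failures that occur between randomization and Step 3. Neither Section 11.2 nor 11.3 states a rate for them.

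If such failures occur at similar rates on both arms, they fill part of the event target with events that do not separate the arms. They pull the average hazard ratio towards 1 and lower power. If the rates differ between arms, the day-84 component becomes part of the treatment contrast and may help or hurt. In either case the single figure of 81% does not show how far the design depends on surgical and Step 3 attrition as opposed to relapse. Section 11.3 carries the figure into a smaller trial without revisiting it.

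**Working it through.** **Inputs.** From Section 11.2: event-free fractions 60% and 70%; medians among the rest 2 and 2.5 years; two-sided alpha 15%; 104 events; average HR 0.64; 250 per arm; 2-year accrual; analysis 1.5 years later. From Section 11.3: 336 participants (168 per arm). Assumed here, because the documents do not give them: the day-84 failure rate q, and a 3-year accrual for the 336.

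**1. Reproducing the 81%.** Schoenfeld's formula: |ln 0.64| × √104 / 2 = 0.446 × 10.20 / 2 = 2.276; less 1.440 gives 0.836, hence power 79.8%. Simulating the stated curves (500 participants, futility look at 51 events, analysis at 3.5 years) gives 80.6%. The stated figure is recovered from the smooth curves alone.

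**2. Events by day 84 in those curves** (84/365.25 = 0.23 years).
- Adjuvant: 0.4 × (1 − 2^(−0.23/2)) = 3.1%, or 7.7 of 250.
- Neoadjuvant: 0.3 × (1 − 2^(−0.23/2.5)) = 1.9%, or 4.6 of 250.

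About 12 of the 104 events fall by day 84, spread smoothly.

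**3. Power with equal day-84 failures.** Two readings are possible. *Added*: failures come on top of the planned event totals of 40% and 30%; at q = 15% the totals become 0.15 + 0.85 × 0.40 = 49% and 0.15 + 0.85 × 0.30 = 40.5%. *Within*: the totals stay at 40% and 30%, and a share q of participants has its event at day 84. Simulated log-rank power, accurate to about 2 points:

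| q per arm | 336 at 104 events, added | 336 at 104 events, within | 500 at 3.5 years, added, before futility |
|---|---|---|---|
| 0% | 75–78% | 77% | 82% |
| 5% | 68% | 73% | 74% |
| 10% | 57% | 67% | 64% |
| 15% | 45% | 62% | 56% |

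For the first power column the average HR is about 0.65, 0.69, 0.73 and 0.77.

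**4. Unequal failures** (336 participants, 104 events).
- 5% adjuvant and 10% neoadjuvant: about 30% power if added, 59% if within.
- 10% adjuvant and 5% neoadjuvant: about 87% if added, 77% if within.

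**5. Section 11.3 on its own curves, with q = 0.** Expected events per arm are n(1 − c)[1 − (e^(−λ(T−A)) − e^(−λT))/(λA)], where c is the event-free fraction, λ = ln 2/median, A the accrual length and T the analysis time. With A = 3 and T = 3.5:
- Adjuvant: 67.2 × [1 − (0.841 − 0.297)/1.040] = 32.1.
- Neoadjuvant: 50.4 × [1 − (0.871 − 0.379)/0.832] = 20.6.

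The total is 53, not 104. Accrual of 2 or 4 years gives 43 or 61. Simulated power at that time (3-year accrual) is about 62%. With unlimited follow-up the curves yield 67.2 + 50.4 = 117.6 events, so 104 is 88% of all the events they can ever produce. In simulation the 104th event comes at a median of 8.4 years from first enrolment, more than 5 years after accrual ends, with power of about 77%.

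**The case against.** The strongest reply is that Section 11.2 labels its inputs as EFS assumptions for this population, so the 60% and 70% may already cover every kind of EFS event. How they were derived is not shown, and the background sentence describes an approval rather than a calculation. This stands in part. It rules out calling 81% an arithmetic error, and it is why both readings are shown. It does not remove the issue: when the failures lie inside the totals, equal rates still lower power, because the smooth curve puts only 3.1% and 1.9% of participants in the first 84 days.

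Four stronger inferences are tempting, and the documents do not support them.

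- *That every participant without surgery or Step 3 is an event.* Section 10.10 exempts confirmed neoadjuvant responders who decline surgery.
- *That power is certainly lost.* No failure rate is given. Fewer failures on the neoadjuvant arm would generally help the test; under the added reading power rises to about 87%.
- *That the design accepts 16% + 5% = 21% early failures on the neoadjuvant arm.* Section 11.5 suspends accrual if the "proportion of participants who become unresectable prior to surgery is greater than 16" percent, or if more than 5% lose surgery to toxicity, at looks after 20, 40 and 60 participants. These are safety triggers, not planning rates, and nothing says both limits would be reached together. With neoadjuvant failures that far above the adjuvant arm's, there might be no EFS benefit left to detect.
- *That the sponsor privately expected many day-84 events.* About 17–18% per arm would bring 104 events within six months of a 3- to 3.5-year accrual. That is one possible explanation of Section 11.3; the documents do not say so.

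**Conclusion.** The concern holds in a limited form. The 81% is right for the stated curves, but those curves are not justified for an endpoint that counts from before surgery and assigns events at day 84. With equal failures of 5% to 15%, power in the 336-participant design falls to about 68–45% (added) or 73–62% (within), against about 77% with none. These figures rest on assumed failure rates, an assumed 3-year accrual and analysis at 104 events. Both the size and the sign of the true effect remain unknown until a rate per arm is stated.

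The inconsistency in Section 11.3 is firmer. It needs no day-84 assumption, only that full events means the 104 of Section 11.2 and that accrual is of ordinary length. At six months after accrual the curves give 43 to 61 events for accrual of 2 to 4 years. Waiting for 104 events roughly preserves the power but not the timing; keeping the timing gives up the power.

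**What to change.** In Sections 11.2 and 11.3:

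1. State an assumed day-84 failure rate for each arm, after the responder exception, and say whether it lies inside the 40% and 30% event totals or is added to them.
2. Replace the single 81% with power and average HR over a small grid, for example 5%, 10% and 15% equal, plus rates that differ by 5 points in each direction.
3. Restate Section 11.3's event count, analysis time and power so that all three follow from the same model and from a stated accrual length.

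The cost is a recalculation and, in most scenarios, a less favourable power statement. The sample size, the endpoint and the test do not change.
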